## 7.2. Interim Analyses and Summaries (OS)

At each OS efficacy analysis time point, the critical boundaries for the group sequential test will be derived from the predefined spending function(s) as described in [Section 5.1](#). The calculations of boundaries will be performed using EAST.

Let  $u(t_1)$  and  $u(t_F)$  denote the upper critical boundaries based on the test statistics  $Z_1$  and  $Z_F$  for efficacy at the interim and the final analysis, respectively.

The critical value  $u(t_1)$  for the interim analysis of OS is determined such as

$$P_0(Z_1 \geq u(t_1)) = \alpha(t_1) ,$$

where  $P_0$  denotes the probability under the null hypothesis and  $\alpha(t_1)$  denotes the  $\alpha$  spent based on the predefined spending function at information fraction  $t_1$  ( $t_1$  is calculated as the ratio of the number of OS events observed at the time of the cut-off for the interim analysis and the total number of OS events targeted for the final analysis).

The boundary for the final efficacy analysis will be calculated such that

$$\alpha(t_1) + P_0(Z_1 < u(t_1), Z_F \geq u_F) = \alpha' \text{ where } \alpha' = 0.002 \text{ or } 0.025 \text{ for the analysis of OS}$$

determined according to the testing strategy described in [Section 5.1.1](#).

As described in [Section 5.1.2](#), if the number of OS events in the final analysis deviates from the target number of OS events, the final analysis criteria will be determined as above taking

into account the actual  $\alpha$  spent at the interim analysis and the actual correlation between the two test statistics  $Z_1$  and  $Z_F$ , so that the overall 1-sided significance level across all analyses and comparisons is preserved at 0.025.

## 9. APPENDICES

### Appendix 1. Immune-Related Adverse Events

The MedDRA PTs and clusters for irAEs are defined in the SRP for PF-06801591.

Immune-related AEs (irAEs) will be identified using a combination of programmatic checks and medical review as outlined in Table 25. This case definition is hierarchical, i.e., each step is only checked for participants and events that have already met the prior step.

**Table 25. Case Definition for irAEs**

Step	Selection Criteria	
1	Adverse Event (AE) selected based on a list of pre-specified MeDRA PTs within clusters. These are included in the SRP. If AE matches the list, then it is included in the next step.	
2	AE onset on or after the first dose of study drug and on or before 90 days after last dose of study treatment.	This is regardless of start of new anti-cancer drug therapy and regardless of TEAE classifications.
3	AE treated with corticosteroids or other immunosuppressant therapy. For endocrinopathies only: AE required hormone replacement.	Look in the conmed pages for AEs where concomitant medications match any of the following A) conmed ATC code is in (H02A, H02B, D07, A01AC, S01BA, S01BB, L04AA, L04AB, L04AC, L04AD, L04AX, A07EA) and AE PT is in any of the irAE clusters. B) conmed ATC code is in (H03A, H03B) and AE PT is in one of the irAE clusters associated with “Immune-mediated endocrinopathies: Thyroid disorders” C) conmed ATC code is A10A and AE PT is in the irAE cluster associated with “Immune-mediated endocrinopathies: Type I Diabetes Mellitus”
4	4A) AE has no clear alternative etiology other than the immune-mediated etiology. OR 4B) AE has a histopathology / biopsy consistent with immune-mediated event.	Steps 4A) and 4B) are assessed by the clinical team based on medical review of the data available in the CRF and SAE report (if applicable). Steps 4A) and 4B) are not completed programmatically.

The data set associated with irAEs may be further refined based on medical review. The final data set including any changes based on medical review will be the basis of the irAE analyses.

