Subsequent Anti-cancer Therapy	X	X	X	X	Start date and other details of anti-cancer therapy (including cystectomy) subsequent to the study treatment will be recorded.
Survival Follow-up				X	Visit is a phone call Q12W. See Section 8.2.6.
Immunogenicity and Pharmacodynamic Biospecimen					
Pharmacokinetics	X				Collect the last PK sample at EOT. If EOT is done on the same date as the last dose of PF-06801591, all efforts should be made to obtain PK samples within 2 hours prior to PF-06801591 dosing. Arms A and B only. See Section 8.5.
Immunogenicity	X				Collect the last immunogenicity sample at EOT. See Section 8.8.3. Arms A and B only.

AE: adverse event; ADA: anti-drug antibodies; BP: blood pressure; CT: computed tomography, ECG: electrocardiogram, EORTC-QLQ-C30: European Organisation for Research and Treatment of Cancer Quality of Life Questionnaire-30 (items); EOT: end of treatment; MRI: magnetic resonance imaging, NAb: neutralizing antibodies; NMIBC: non-muscle invasive bladder cancer, PGIC: Patient Global Impression of Change; PGIS: Patient Global Impression of Severity; PK: pharmacokinetics, PTAB: Patient Treatment Administration Burden; SAE: serious adverse event; TSQ: Treatment Satisfaction Questionnaire

Screening and Treatment Period – Cohorts B1 and B2

	Screening	Treatment Period	Notes
		Cycles 1-25 (Cohort B1) Cycles 1-17 (Cohort B2)	Cohort B1: Cycle = 4 weeks Cohort B2: Cycle = 6 weeks
	D -28 to D -1	D1	
Visit Window (Days)		±0 (C1) ±7 C2-25 [Cohort B1] C2-C17 [Cohort B2]	
Informed Consent	X	X	Informed consent may be obtained more than 28 days prior to start of study treatment. All screening procedures must be completed within 28 days of registration. The Consent for continuation of treatment at 12 weeks for those participants in Cohort B1 with persistent CIS and Consent for future research will be signed as applicable. Participants must sign consent prior to any trial-specific procedure. See Section 10.1.3.
Tumor and Medical History	X		Detailed information about prior BCG usage, response to prior BCG, and details regarding disease persistence or recurrence will be collected in the CRF. Reasons for subject ineligibility or refusal of radical cystectomy will also be collected. See Section 8 for details.
Physical Examination	X	X	Physical examinations should be performed according to clinical practice. Any abnormalities should be recorded as AEs. See Section 8.2.1.
Weight	X	X	

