8.3.1. Time Period and Frequency for Collecting AE and SAE Information

The time period for actively eliciting and collecting AEs and SAEs (“active collection period”) for each participant begins from the time the participant provides informed consent, which is obtained before the participant’s participation in the study (ie, before undergoing any study-related procedure and/or receiving study intervention), through and including a minimum of 90 calendar days after the last administration of the study intervention.

For participants who are screen failures, the active collection period ends when screen failure status is determined.

Follow-up by the investigator continues throughout and after the active collection period and until the AE or SAE or its sequelae resolve or stabilize at a level acceptable to the investigator and Pfizer concurs with that assessment.

For participants who are screen failures, the active collection period ends when screen failure status is determined.

If the participant withdraws from the study and also withdraws consent for the collection of future information, the active collection period ends when consent is withdrawn.

If a participant definitively discontinues or temporarily discontinues study intervention because of an AE or SAE, the AE or SAE must be recorded on the eCRF and the SAE reported using the CT SAE Report Form.

Investigators are not obligated to actively seek AEs or SAEs after the participant has concluded study participation. However, if the investigator learns of any SAE, including a death, at any time after a participant has completed the study, and he/she considers the event to be reasonably related to the study intervention, the investigator must promptly report the SAE to Pfizer using the CT SAE Report Form.

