8.3.1.2. Recording Nonserious AEs and SAEs on the eCRF

All nonserious AEs and SAEs occurring in a participant during the active collection period, which begins after obtaining informed consent as described in Section 8.3.1, will be recorded on the AE section of the eCRF.

The investigator is to record on the eCRF all directly observed and all spontaneously reported AEs and SAEs reported by the participant.

If a participant begins a new anticancer therapy, the recording period for nonserious AEs ends at the time the new treatment is started; however, SAEs must continue to be recorded on the eCRF during the above-indicated active collection period. Note that a switch to a commercially available version of the study intervention is considered as a new anticancer therapy for the purposes of SAE reporting.

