8.3.8. Adverse Events of Special Interest

Any AE that is suspected to be a potential irAE is considered an AE of special interest (AESI). Specific guidance for the management of irAEs is provided in Section 10.13. All AESIs must be reported as an AE or SAE following the procedures described in Sections 8.3.1 through 8.3.4. An AESI is to be recorded as an AE or SAE on the eCRF. In addition, an AESI that is also an SAE must be reported using the CT SAE Report Form.

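### The irAE window in SAP Table 25 runs to 90 days after last dose whatever therapy follows, but the protocol stops recording nonserious AEs when new anticancer therapy starts

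*SAP*

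**What the plan says.** SAP Appendix 1 identifies irAEs through a hierarchical case definition (Table 25). Step 1 selects AEs from a prespecified term list. Step 2 sets the time window: "AE onset on or after the first dose of study drug and on or before 90 days after last dose of study treatment". The note beside it reads: "This is regardless of start of new anti-cancer drug therapy and regardless of TEAE classifications". SAP 6.6.4.1 then tabulates irAEs by cluster, preferred term and worst grade, by any grade and Grade 3 or higher, and separately those that are serious or lead to death. It also tabulates potential irAEs, meaning events that pass Steps 1 and 2.

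Protocol 8.3.1 sets a general active collection period that runs "through and including a minimum of 90 calendar days after the last administration of the study intervention". Section 8.3.1.2 shortens it for some events: "If a participant begins a new anticancer therapy, the recording period for nonserious AEs ends at the time the new treatment is started". For serious events the rule differs: "SAEs must continue to be recorded on the eCRF during the above-indicated active collection period".

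Protocol 8.3.8 makes any suspected irAE an adverse event of special interest (AESI). It states: "All AESIs must be reported as an AE or SAE following the procedures described in Sections" 8.3.1 through 8.3.4. That range includes 8.3.1.2, and no exception is given.

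**The concern.** The SAP defines an analysis window that the protocol does not fully collect. Step 2 makes no distinction between serious and nonserious events, while the protocol's recording rule does. A reader of the worst-grade table would take it to cover all irAEs for 90 days after last dose. For anyone who moved to another therapy inside that period, a nonserious irAE with later onset, including a nonserious Grade 3 event, need not be in the database.

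irAEs are one of the two AESI categories named in SAP 3.5.1, and these tables are a main description of the antibody's safety. The missing observation is also unlikely to be random. Recurrence, progression and persistent CIS are reasons for stopping treatment (protocol 7.1), and participants who stop for them are natural candidates for further therapy. At stake is whether the tables describe their own coverage correctly. No efficacy conclusion is involved.

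**Working it through.** The plan states no figure to reproduce. The check sets the collection rule against the analysis rule and looks for a provision that would reconcile them.

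**1. Coverage by type of event.** Let t be the number of days from last dose to the start of new anticancer therapy.

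| Event | SAP Step 2 counts onset to | Protocol requires recording to |
|---|---|---|
| Serious irAE, any participant | day 90 | at least day 90 |
| Nonserious irAE, no new therapy by day 90 | day 90 | at least day 90 |
| Nonserious irAE, new therapy at t < 90 | day 90 | day t |

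Only the last row disagrees. The nonserious observation lost is 90 − t days, which can be anything from 0 to nearly 90. Two assumed values illustrate the formula: t = 28 gives 90 − 28 = 62 days (62/90 = 69%), and t = 56 gives 90 − 56 = 34 days (34/90 = 38%). The documents do not give the distribution of t or the number of participants with t < 90.

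**2. Search for a cure.**
- The 90-day period in protocol 8.3.1 is the general rule. Section 8.3.1.2 is the specific rule that shortens it for nonserious events.
- Protocol 8.3.8 sends AESIs through the same sections and grants no exemption.
- The Schedule of Activities has safety visits at 30, 60 and 90 days after end of treatment, but its AE row refers back to section 8.3.
- Concomitant treatments are recorded to the end of safety follow-up (protocol 6.5). This does not help, because Table 25 is hierarchical and Step 1 needs an AE record. A steroid course without a recorded AE never becomes an irAE.

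**3. Comparison within the SAP.** The on-treatment period for TEAEs (SAP 3.5.1 and 5.2.7) ends at the earlier of 30 days after last dose and the day before new anti-cancer drug therapy. The TEAE tables therefore already stop at new drug therapy. Only the irAE definition overrides that, and it does not mention the recording limit.

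**4. Tables affected.** Exposed: irAEs by worst grade, irAEs of any grade and Grade 3 or higher, the irAE line in the overall AE summary (SAP 6.6.1.1), and potential irAEs. Not exposed: serious irAEs and irAEs leading to death, since these are SAEs.

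**5. Can collection still be changed?** SAP section 2 gives 16 November 2023 as the end of the treatment period. Adding 90 days (14 left in November, 31 in December, 31 in January, 14 in February) gives 14 February 2024. That is before protocol amendment 5 (17 June 2024) and SAP version 8 (10 December 2024). It cannot.

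**The case against.** The best defence is that Step 2 only filters the onset dates of AEs that were recorded. SAP 6.6.4.1 reports numbers and percentages of participants, with no person-time and no 90-day follow-up denominator. A reader might infer that the SAP credits every participant with 90 complete days; it does not say so. That stands, but the stated window still invites that reading, and nothing in the SAP corrects it.

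A second defence is that much is already protected. Serious irAEs are recorded throughout, and subsequent therapies are tabulated by arm and listed (SAP 6.5.5), so the participants concerned can be identified. An event is lost only if it is nonserious, starts after new therapy, is on the term list and would also have passed Steps 3 and 4. This limits the likely size and also stands.

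Three stronger readings are tempting and not supported:
- **Known bias in the antibody arms.** Nonserious irAEs may be undercounted in any arm. If the antibody delays disease events, Arm C could have more truncated participants than Arms A and B. The documents do not settle the net effect on a comparison.
- **A count taken from the expected events.** About 261 EFS events are expected among 1056 randomized participants (24.7%). They include deaths, Arm C and events that may fall long after day 90, so they do not give the number truncated.
- **Cystectomy certainly stops recording.** The protocol lists cystectomy under subsequent anti-cancer therapy in the Schedule of Activities and in 8.2.6, but 8.3.1.2 does not define its trigger. If surgery counts, the gap is wider than the drug-therapy wording of Step 2 suggests. This is an inference.

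**Conclusion.** The mismatch is real and nothing in either document removes it. For participants who start new anticancer therapy within 90 days of last dose, the irAE tables that include nonserious events are assured of serious events only from that point on. For all other participants, and in the serious and fatal irAE tables, the stated window agrees with the collection rule.

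The size is between zero and nearly 90 days of nonserious observation per affected participant. The number of such participants is not given, and neither it nor the direction by arm can be derived. The conclusion assumes that sites followed 8.3.1.2 as written. If some went on recording nonserious events after new therapy, coverage would be uneven, and the tables would still need a statement of it. This is a correction to safety reporting that should be made; the efficacy analyses are untouched.

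**What to change.** Change the SAP only:

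1. Keep the Step 2 table. State in Appendix 1 and in the footnotes of the irAE tables that, once a new anticancer therapy has started, only serious irAEs are required to be recorded.
2. Add an irAE table, serious and nonserious together, cut at the earlier of 90 days after last dose and the day before new anti-cancer drug therapy as defined in SAP 5.2.5. Do not use the date in SAP 5.2.6. That date runs from randomization and includes on-study resections, while protocol 6.5.7 allows TURBT during the study and 4.1.1 allows BCG re-induction and maintenance afterwards. A cut there could discard valid nonserious irAEs in participants still on treatment.
3. Report by arm how many participants started new therapy within 90 days of last dose, by type of therapy, with the days of nonserious observation lost (90 − t). Splitting by type shows how far the answer depends on whether surgery or radiation counts as a trigger.

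No protocol change is proposed, because the collection period has closed. The cost is a footnote, derived dates from data already collected, one extra irAE table and a short count by arm. The downside is a less favourable statement of how long nonserious irAEs were observed.

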10.13. Appendix 13: Management of Immune-related Adverse Events (irAEs)

Gastrointestinal irAEs		
Severity of Diarrhea/Colitis (NCI-CTCAE v5.0)	Initial Management	Follow-up Management
Grade 1 Diarrhea: < 4 stools/day over Baseline Colitis: asymptomatic	-Continue study treatment -Symptomatic treatment (eg loperamide)	-Close monitoring for worsening symptoms. -Educate participant to report worsening immediately. -If worsens: Treat as Grade 2, 3 or 4.
Grade 2 Diarrhea: 4 to 6 stools per day over Baseline; IV fluids indicated < 24 hours; not interfering with ADL Colitis: abdominal pain; blood in stool	-Withhold study treatment -Symptomatic treatment	-If improves to Grade ≤ 1: Resume study treatment. -If persists > 5-7 days or recurs: Treat as Grade 3 or 4.
Grade 3 to 4 Diarrhea (Grade 3): ≥ 7 stools per day over Baseline; incontinence; IV fluids ≥ 24 hours; interfering with ADL Colitis (Grade 3): severe abdominal pain, medical intervention indicated, peritoneal signs Grade 4: life-threatening, perforation	-Withhold for Grade 3 -Permanently discontinue study treatment for Grade 4 or recurrent Grade 3 -1.0 to 2.0 mg/kg/day prednisone IV or equivalent -Add prophylactic antibiotics for opportunistic infections -Consider lower endoscopy	-If improves: -Continue steroids until Grade ≤ 1, then taper over at least 1 month; resume study treatment following steroids taper (for initial Grade 3). -If worsens, persists > 3 to 5 days, or recurs after improvement. -Add infliximab 5 mg/kg (if no contraindication). -Note: infliximab should not be used in cases of perforation or sepsis.

Dermatological irAEs		
Grade of Rash (NCI-CTCAE v5.0)	Initial Management	Follow-up Management
Grade 1 to 2 Covering \leq 30% body surface area	-Continue study treatment -Symptomatic therapy (for example, antihistamines, topical steroids)	-If persists $>$ 1 to 2 weeks or recurs: -Withhold study treatment -Consider skin biopsy -Consider 0.5-1.0 mg/kg/day prednisone or equivalent. Once improving, taper steroids over at least 1 month, consider prophylactic antibiotics for opportunistic infections, and resume study treatment following steroids taper. -If worsens: Treat as Grade 3 to 4.

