Grade 2 AST or ALT > 3.0 to \leq 5 x ULN and/or total bilirubin > 1.5 to \leq 3 x ULN	-Withhold study treatment -Increase frequency of monitoring to every 3 days	-If returns to Grade \leq 1: -Resume routine monitoring; resume study treatment. -If elevation persists > 5 to 7 days or worsens: -Treat as Grade 3 to 4.
Grade 3 to 4 AST or ALT > 5 x ULN and/or total bilirubin > 3 x ULN	-Permanently discontinue study treatment -Increase frequency of monitoring to every 1 to 2 days -1.0 to 2.0 mg/kg/day prednisone or equivalent -Add prophylactic antibiotics for opportunistic infections -Consult gastroenterologist/hepatologist -Consider obtaining MRI/CT scan of liver and liver biopsy if clinically warranted	-If returns to Grade \leq 1: -Taper steroids over at least 1 month. -If does not improve in > 3 to 5 days, worsens or rebounds: -Add mycophenolate mofetil 1 gram (g) twice daily. -If no response within an additional 3 to 5 days, consider other immunosuppressants per local guidelines.

Renal irAEs		
Grade of Creatinine Increased (NCI-CTCAE v5.0)	Initial Management	Follow-up Management
Grade 1 Creatinine increased > ULN to 1.5 x ULN	-Continue study treatment	-Continue renal function monitoring. -If worsens: Treat as Grade 2 to 3 or 4.
Grade 2 to 3 Creatinine increased > 1.5 and \leq 6 x ULN	-Withhold study treatment -Increase frequency of monitoring to every 3 days -1.0 to 2.0 mg/kg/day prednisone or equivalent. -Add prophylactic antibiotics for opportunistic infections -Consider renal biopsy	-If returns to Grade \leq 1: -Taper steroids over at least 1 month, and resume study treatment following steroids taper. -If worsens: -Treat as Grade 4.
Grade 4 Creatinine increased > 6 x ULN	-Permanently discontinue study treatment -Monitor creatinine daily -1.0 to 2.0 mg/kg/day prednisone or equivalent. -Add prophylactic antibiotics for opportunistic infections Consider renal biopsy -Nephrology consult	-If returns to Grade \leq 1: Taper steroids over at least 1 month.

Cardiac irAEs		
Myocarditis	Initial Management	Follow-up Management

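### Grade 2 diarrhoea/colitis and hepatic events that resolve on withholding alone, with no steroid or other immunosuppressant, drop out of the SAP's graded irAE tables

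*SAP*

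**What the plan says.** SAP Appendix 1 states: "This case definition is hierarchical, i.e., each step is only checked for participants and events that have already met the prior step". Table 25 then sets four steps:

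1. The preferred term is on a pre-specified list held in the Safety Review Plan.
2. Onset lies between first dose and 90 days after last dose of study treatment, whatever the treatment-emergent status and whether or not a new anti-cancer drug has started.
3. "AE treated with corticosteroids or other immunosuppressant therapy", or, for endocrinopathies only, hormone replacement.
4. The clinical team finds no clear alternative cause, or a consistent biopsy.

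A closing note lets medical review refine the irAE data set.

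SAP 6.6.4.1 tabulates irAEs by cluster and preferred term, with worst grade, seriousness, death and discontinuation. For potential irAEs (Steps 1 and 2 only) it plans a participant frequency by arm and says no more.

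Protocol Appendix 13 gives the initial management of Grade 2 diarrhoea/colitis as "Withhold study treatment -Symptomatic treatment", and of Grade 2 liver test elevation as "Withhold study treatment -Increase frequency of monitoring to every 3 days". Neither entry lists a steroid.

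On events of special interest, protocol 8.3.8 says "Any AE that is suspected to be a potential irAE is considered an AE of special interest (AESI". SAP 3.5.1 limits the term to irAEs as classified by Appendix 1, plus injection site reactions related to PF-06801591.

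**The concern.** Step 3 uses a treatment decision as a gate on case status. In two organ classes the protocol's first-line Grade 2 management contains no treatment that opens that gate. A participant can have PF-06801591 withheld for a suspected irAE, recover, resume as Appendix 13 directs, and not be counted. Step 4, where cause or biopsy is judged, is never reached.

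The gate does not follow severity either. Step 3 as worded sets no limit on the route of the corticosteroid, and Appendix 13 lists topical steroids for Grade 1-2 rash while study treatment continues. Such a rash can pass Step 3 where colitis that interrupted dosing does not.

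Protocol 2.3 names irAEs as important risks of PF-06801591. At stake is whether the tables read as the irAE profile of Arms A and B against BCG alone include a class of dose-interrupting events.

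**Working it through.** The plan states no figure to reproduce, so the check follows each management path through Table 25. All rows assume a listed preferred term and onset inside the 90-day window.

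| Grade 2 event | Protocol Appendix 13 | Step 3 | Graded irAE tables | Step 1-2 frequency |
|---|---|---|---|---|
| Diarrhoea/colitis, improves to Grade ≤1 on withholding and symptomatic care | Resume | Fails if no listed drug is given | No | Yes |
| Diarrhoea/colitis, persists or recurs | "If persists > 5-7 days or recurs: Treat as Grade 3 or 4"; that row gives "1.0 to 2.0 mg/kg/day prednisone IV or equivalent" | Can be met | Yes, if Step 4 is met | Yes |
| Hepatic, returns to Grade ≤1 on withholding and closer monitoring | Resume | Fails if no listed drug is given | No | Yes |
| Hepatic, persists more than 5 to 7 days or worsens | Grade 3-4 row, prednisone 1.0 to 2.0 mg/kg/day | Can be met | Yes, if Step 4 is met | Yes |

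Only rows 1 and 3 are affected. Protocol 6.5.6 also foresees immune suppressive treatment by local practice when irAEs occur, so some events in those rows will receive a steroid and pass.

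**Where the lost events still show.** SAP 6.6.1.1 gives treatment-emergent events by system organ class, preferred term and worst grade. SAP 6.6.1.3 gives those leading to interruption of each drug. SAP 6.6.3 gives serious events, and SAP 6.6.5.1 gives transaminase and bilirubin thresholds. None of these depends on Step 3, and none groups events into irAE clusters.

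**Time window.** Under SAP 5.2.7 the on-treatment period ends 30 days after last dose, or the day before a new anti-cancer drug if that is sooner. Safety data outside it are listed but not summarised. The irAE window ends at 90 days. For onset in the remaining 90 − 30 = 60 days (days 31 to 90), an event failing Step 3 is summarised only in the potential-irAE frequency.

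**Scale, by assumption only.** With 1056 randomised 1:1:1, Arms A and B together hold about 1056 × 2/3 = 704. The documents give no rate of steroid-free Grade 2 gastrointestinal or hepatic irAEs for this drug. If 2% to 5% of participants had one, 704 × 0.02 = 14 to 704 × 0.05 = 35 participants would be missing from the graded irAE tables.

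**The case against.** The strongest reply has four parts.

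- **The events are not hidden.** The interruption, graded adverse event and liver tables show most of them by arm. This stands for onset within the on-treatment period. It does not supply irAE clusters, and it does not cover days 31 to 90.
- **Withholding does not confirm immune cause.** For other irAEs, Appendix 13 withholds drug while the cause is investigated and allows that an irAE may be ruled out. Appendix 14 treats persistent liver test abnormalities as a possible sign of systemic BCG infection, and BCG is given in every arm. Step 3 can be defended as a choice for specificity, with the Step 1-2 frequency as its sensitive counterpart. This stands, and is why Table 25 should be kept. The counterpart is simply not specified in enough detail to serve.
- **The term list is not in these documents.** If diarrhoea or isolated enzyme elevation is not listed, Step 1 removes the event and Step 3 is irrelevant. This stands as a limit on the size.
- **Protocol 8.3.8 is an instruction to sites, not an analysis definition.** That is a fair reading, but the SAP uses the same label for a different set of events.

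The medical-review clause does not settle the matter. It does not say whether events that failed Step 3 may be added back.

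**Conclusion.** The point holds for a defined subset: Grade 2 diarrhoea/colitis and Grade 2 hepatic events that resolve on withholding alone, with no Step 3 drug given. They are absent from every graded irAE table, and their only irAE-labelled summary is the Step 1-2 frequency. The graded tables may therefore understate irAE incidence. The amount cannot be derived from the documents; the 14 to 35 above rests wholly on an assumed 2% to 5%.

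A reader might infer two stronger things. One is that no such Grade 2 event can qualify when managed as the protocol directs. That is not supported, because the directed management itself escalates persistent, recurrent (gastrointestinal) or worsening (hepatic) events to prednisone. The other is that the difference between Arms A or B and Arm C is biased low by a known amount. That is not supported either: the rates and the immune cause of the omitted events are unknown, and much of the information is displayed elsewhere. This is a gap in presentation and definition, worth closing because it is cheap to close.

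**What to change.** 1. In SAP 6.6.4.1, keep the Table 25 definition and its tables. Add, by arm, tables of Step 1-2 potential irAEs by cluster, preferred term and worst grade; serious; and leading to interruption or discontinuation of any study drug.
2. In Appendix 1, state whether medical review may reinstate events that fail Step 3.
3. Reconcile the special-interest definitions in protocol 8.3.8 and SAP 3.5.1.

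Do not widen Step 3 with a route based on interruption of PF-06801591. Arm C receives BCG only and could never meet it, so ascertainment would differ by arm.

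The cost is SAP wording and a few tables from action-taken, grade and seriousness data already on the adverse event eCRF. The downside is a second, less specific irAE rate that must be labelled as such. No change to clinical management is implied.
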